#### **6.2.4 Secondary Efficacy Analysis**

Other efficacy variables analysed include: Mortality rates, Days free of Mechanical ventilation (actual days not VFD calculated days), Days free of Organ Failure, Renal Support And Vasoactive Support, Length Of ICU 'Care Free' Stay/Hospital Stay, Sequential Organ Failure Assessment (SOFA) and Other Individual Organ Assessments

##### **6.2.4.1 Mortality Analysis**

The Mortality rate is principally assessed during the Short Term Follow Up in the hospital at Day 28. However, the mortality rates occurring within the ICU and in the hospital will be calculated separately using the location of the death. The Overall mortality rate irrespective of location will be analysed.

The observed Mortality rates (with 95% Confidence Intervals (Clopper Pearson)) for each Treatment group (FP-1201-lyo and Placebo) and the Treatment difference (FP-1201-lyo - Placebo) will be displayed using categorical summarises (Alive/Dead) according to Severity of ARDS (Moderate/Severe) and Overall according to the FAS population. Separate supporting summaries by Country will be included.

The binary mortality endpoint outcome (Alive/Dead) will be modelled using logistic regression applied (Ref 6) to the FAS population. The model will include Treatment group (FP-1201-lyo/Placebo), Severity of ARDS (Moderate/Severe) and Country (1-8) as factors.

Homogeneity of treatment effect will be assessed by calculating ORs and associated confidence intervals by ARDS severity and by country and displaying these in a Forest Plot (log scale).

The analysis will primarily use the FAS population but this will be repeated using the PPS group as supporting information.

Other baseline characteristic variables potentially contributing to sources of variability may be included in further sensitivity analyses.

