#### 7.2.2.2 *Pre-dose Procedures to Be Performed on D1 Before the First Dose of Study Drug is Administered*

**Note:** Prior to the first administration of any study drug on D1, the patient's moderate or severe ARDS status (as per Inclusion Criterion 1 in Section 4.1) must be confirmed. That the patient continues to be on mechanical ventilation must also be confirmed. If both criteria are not confirmed, the patient should be withdrawn from the study and will be classed as a screen failure.

On D1 all pre-dose procedures and assessments are to be performed **before the first dose of study drug**.

The following procedures and assessments will be performed:

- Review of the inclusion and exclusion criteria to ensure continued eligibility, including a check that the patient is in the ICU and on ventilation
- Check PaO2/FiO2 ratio
- Randomisation: randomisation number and date and time of randomisation will be recorded
- SOFA scoring will be done pre-dose based on the worst value so far that day for each of the following parameters:
  - PaO2/FiO2 (mmHg)
  - platelets × 10^3/mm^3
  - bilirubin (µmol/L or mg/dL)
  - hypotension/use of vasopressors
  - GCS
  - creatinine (µmol/L or mg/dL) or urine output
- APACHE II scoring will be done on the worst values in the 24 hours following ICU admission or up to the time of the first dose if the patient has been on the ICU less than 24 hours (see Table 4).
- The following ventilation variables should be recorded in the morning between 04:00 to 10:00 using the values closest to 10:00 (if these values are representative of the patient's condition), whenever possible:
  - Mode of ventilation (whether predominantly volume or pressure set)
  - Tidal volume (ml)
  - Respiratory rate (breaths per min) - total respiratory rate will be used if the patient is breathing spontaneously on a mechanical ventilator
  - Peak inspiratory pressure (cmH2O)
  - Plateau pressure (cmH2O) - if set
  - Mean airway pressure (cmH2O)
  - PEEP

- All ventilator assessments must be taken at the same time point whenever possible and should be representative of the values over the recent past. PEEP is not available if using HFOV.
- Recording of vasoactive drugs and renal support
- Perform ECG

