### 8.5.2 Secondary Efficacy Analyses

#### 8.5.2.1 All-cause Mortality

As confirmatory measures of efficacy, the following endpoints will be analysed:

- Mortality up to D28, up to D90 (3 months) and up to D180 (6 months)
- Mortality in ICU up to D28
- Mortality in hospital up to D28

The primary analysis of the binary mortality endpoints will be based on the FAS and will be undertaken using logistic regression adjusting for country, ARDS severity and key baseline characteristics. This analysis will be repeated using the PPS as a sensitivity analysis. Each of these analyses will be summarised using the observed mortality rates for the two treatment groups, a 95% confidence interval (CI) for the difference in these rates, an adjusted odds ratio and a 95% CI for the adjusted odds ratio. A two-sided significance level of 0.05 will be used for each of these endpoints.

There will also be an evaluation of the homogeneity of the treatment effect by investigating treatment by country, treatment by ARDS severity, and treatment by baseline factor interactions in the logistic model. Data for these efficacy endpoints will also be presented for key predefined subgroups of patients together with 95% CIs for the difference in those rates to supplement the investigation of homogeneity.

ICU mortality and hospital mortality will be analysed in the same way as overall mortality.

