### ***5.2.1 Admission***

At Admission to the ICU they include details of: Status including Intubation, Renal support, Body position and any required Vasoactive infused drug treatment.

These are then supported by a combined assessment of Acute physiology and Chronic health to derive an APACHE II score (0-71) to additionally classify the severity of the condition.

Demographics (Age, Race, Sex) are then supplemented with details of the Disease diagnosis and Aetiology supported by Imaging (Chest X-ray / CT scan) and Ventilation evidence (Gas exchange variables). Aetiology is categorised as: Pancreatitis, Trauma/Burns, Sepsis, Multiple Transfusion, Aspiration, Pneumonia or Other. If the cause is Sepsis then the site of infection is noted.

Following satisfactory completion of all the Inclusion/Exclusion criteria details (including a negative pregnancy test for females) Medical history (including any relevant previous and ongoing medical conditions) is recorded together with Prior medications (taken in the last 30 days but stopped before signing Informed consent) and a complete Physical examination (with predicted body weight).

Ongoing medications are recorded as Concomitant Medications (classified as either Bolus or Infusion) and reported accordingly if started prior to treatment dosing (Day 1). Any medication given with or after the first injection of study drug is also classified as a concomitant treatment.

Prior to the start of dosing on Day 1 the Patient status and Inclusion/Exclusion criteria are confirmed and all Medications are updated.

A series of Baseline safety assessments are then performed. These include: Safety laboratory tests (Biochemistry, Haematology, Urinalysis), Vital signs, 12 Lead ECG and Ventilation (Gas exchange). Specific variables measured are listed in section 5.8.

Baseline efficacy assessments performed are: the System Organ Failure SOFA score and Quality of Life (EQ-5D-3L) assessment. Details of the specific variable items measured are given in section 5.3.3.5 and 5.4.2 respectively.

Pre-dose blood samples are taken for pharmacodynamic baseline assessment. These include: Myxovirus Resistance Protein A (MxA), CD 73 biomarker, Potential Inflammatory Markers (PIMs). Also a sample for Anti Drug Antibodies (ADA) and Neutralising Antibodies (NABs) to Interferon Beta-1a assessment will be taken. A tier based approach for the NABs analyses will be used where NABs will be assessed only if ADAs exists.

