### ***5.9.5 Strategy For Assessing Sources Of Variability***

Both the Country and Severity of ARDS are considered major sources of variability and potentially influencing factors on the magnitude of the treatment effect. Both are included as strata in the randomisation process. All analyses will include these as factors in statistical models or classification strata for hypothesis tests in order to ensure the precision of estimates obtained.

Recruitment of patients to individual sites within each of the countries is likely to be highly variable. However, although the process of pooling of patients within country should produce a more uniform distribution this will be monitored. In the event of low recruitment in some countries then country pooling strategies may need to be investigated in order to minimise variability. Decisions regarding pooling will take place at the Blind Review.

The impact of patient variability on the Severity of ARDS (Moderate, Severe) will also be explored.

As the adjustment for covariates increases the precision of estimates in proportion to correlation with outcome measure, demographic and other baseline patient data will also be assessed as additional sources of potential variability. Identified variables will be included in the statistical models to evaluate the sensitivity and robustness of the magnitude of the treatment effects determined in the main analyses.

Sources of variability will be assessed at the Blind Data Review prior to database lock at Day 90 and subsequent unblinding. These will include but not limited to the following baseline variables: age, race, sex, Apache score, SOFA score, disease diagnosis, aetiology (including presence/absence of shock), country, PaO2/FiO2 ratio, plateau pressure, tidal volume, PEEP, mode of ventilation, respiratory rate, vasoactive drug use, renal support, patient position, comorbidities from MH coding, season (quarter), study stage, arterial pressure, arterial pH, weight (BMI), renal/liver biochemistry (creatinine, CK, AST, ALT). If other variables are assessed during the blinded review, these will be described in the Day 90 statistical analysis report.

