### ***6.1.3 Multiplicity Of Testing***

In view of the number of statistical tests employed to assess the secondary efficacy endpoints measured, a hierarchical approach will be employed which ranks the endpoints in order of importance to control for the multiplicity of testing.

The pre-specified hierarchy for the secondary endpoints is:

1. Mortality (All-cause) at Day 28
2. Mortality in ICU at Day 28
3. Mortality in hospital at Day 28
4. Overall Mortality at Day 360

The process will involve declaring statistical significance down to the first non-significant endpoint (based on a two-sided significance level of 0.05). However, all p-values will be presented and those that are  $\leq 0.05$  but below a non-significant endpoint in the hierarchy will be considered as nominally significant but not formally significant.

Mortality during the follow up period (Day 90, 180 and 360) is considered secondary and included as part of the Kaplan-Meier survival analysis.

All other statistical hypothesis testing applied and p-values generated during the exploratory or safety evaluations will only be used as indicators of potential interest or concern requiring clinical expert commentary.

A two-sided significance level of 5% (0.05) will be used throughout, although in line with standard practice this may be relaxed to 10% when investigating potential model interactions.

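### The SAP's main Day 28 mortality model omits the protocol's baseline covariates without noting the change, and so forgoes power that a prognostic score would give

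*SAP*

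**What the plan says.** Protocol 8.5.2.1 (All-cause Mortality) sets the primary analysis of the binary mortality endpoints as "logistic regression adjusting for country, ARDS severity and key baseline characteristics" on the FAS. Neither document gives a fixed list of those characteristics.

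SAP 6.2.4.1 (Mortality Analysis) specifies the model in full: "The model will include Treatment group (FP-1201-lyo/Placebo), Severity of ARDS (Moderate/Severe) and Country (1-8) as factors". It then adds: "Other baseline characteristic variables potentially contributing to sources of variability may be included in further sensitivity analyses".

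SAP 5.9.5 gives the general strategy. It argues for covariates: "As the adjustment for covariates increases the precision of estimates in proportion to correlation with outcome measure". Its candidates for the Blind Data Review include "the following baseline variables: age, race, sex, Apache score, SOFA score, disease diagnosis" and many more. There the SAP says that variables so identified *will* enter models, but for testing the sensitivity and robustness of the main results.

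SAP 5.2.1 uses acute physiology and chronic health "to derive an APACHE II score (0-71) to additionally classify the severity of the condition". Protocol 7.2.2.2 takes that score from the "worst values in the 24 hours following ICU admission or up to the time of the first dose", so it is a pre-dose measurement.

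The first entry in the SAP 6.1.3 hierarchy is "Mortality (All-cause) at Day 28". It is also first in Protocol 8.5.2.1.1.

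**The concern.** The protocol puts a covariate term in the main mortality model, and the SAP moves it to supporting analyses. The SAP says it is based on protocol version 6.0, has no section on changes from the protocol, and does not call this a departure. Its commitment in Section 1 to document changes covers those made after lock and unblinding.

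This matters because Day 28 mortality heads the secondary hierarchy: if it is not significant, nothing below it can be formally significant. A covariate used only in a sensitivity analysis cannot help that test. If the two plans stay unreconciled, there is also room to argue after unblinding about which mortality p-value is the main one.

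**Working it through.** **1. The plan's own figure.** Protocol 8.10 needs 272 evaluable patients for 90% power (two-sided 0.05, Mann-Whitney) on VFDsurv.
- Control: 30% dead, 20% alive with zero VFD, and the other 50% spread over 28 days, 50/28 = 1.79% per day. Mean VFD = (0.50/28) × 406 = 7.25, where 406 = 1 + 2 + ... + 28.
- Active: mean 7.25 + 3.0 = 10.25, so 10.25/406 = 2.52% per day. Alive with zero VFD = 85% − 28 × 2.5246% = 14.3%. Table 6 shows 2.5% and 14%.
- The tie-corrected Mann-Whitney approximation gives a win probability of 0.610, 89.2% power at 272, and a minimum N of 280. The planned 272 is reproduced within 3%, and it does not depend on the mortality model.

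**2. Power of the mortality test.** No power is stated for it. With n per arm and p̄ the mean of the two rates:

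power = Φ{ [|p1 − p2| − 1.96 √(2p̄(1 − p̄)/n)] / √([p1(1 − p1) + p2(1 − p2)]/n) }

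For 30% vs 15% and n = 136: (0.15 − 1.96 × 0.0506)/0.0498 = 1.02, giving 84.6%. At n = 150 it is 87.9%. For 30% vs 18% (an alternative in Table 6) it is 64.1% and 68.4%.

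**3. Effect of one continuous score.** I simulated the SAP logistic model with and without a standard normal baseline score (Wald test). Assumed: 1:1 blocks of 4 within severity by country, 30% severe, eight countries with shares of 4-25%, modest severity and country effects. The AUC for death is an assumption, shown as a range. Results for 30% vs 15%, N = 272, 16,000 trials per setting (gains taken before rounding):

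| AUC | SAP model | plus score | gain (points) |
|---|---|---|---|
| 0.50 | 86.2% | 86.2% | 0.0 |
| 0.59 | 86.6% | 87.2% | +0.6 |
| 0.64 | 85.9% | 87.5% | +1.7 |
| 0.70 | 86.0% | 88.9% | +2.9 |
| 0.74 | 86.0% | 90.5% | +4.5 |
| 0.78 | 85.7% | 92.3% | +6.6 |

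Other assumptions (35% severe with log odds ratio 0.5, eight equal countries with no country effect, 8,000 trials) give 85.1 to 86.2% at AUC 0.63, 84.7 to 87.6% at 0.70 and 85.4 to 91.2% at 0.77.

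At N = 300, which the FAS could approach because SAP 5.3.3.1 counts missing status as alive, the gains at AUC 0.64, 0.70 and 0.78 are +1.7, +2.8 and +5.3 points from about 89%. For 30% vs 18% at N = 272 they are +2.2, +4.3 and +9.5 points from about 66%.

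**4. Checks on the change.**
- Type I error at 30% vs 30%: 5.1-5.3% without the score, 5.1-5.4% with it.
- At AUC 0.70 the 95% interval for the log odds ratio widens from 1.24 to 1.32, while the median odds ratio moves from 0.39 to 0.35. The gain is in power, not in a narrower interval.
- With 10% or 20% of scores missing and set to the median over both arms, the gain at AUC 0.70 is +2.9 or +2.4 points.
- Expected deaths: 136 × 0.30 + 136 × 0.15 = 61.2. The SAP model has 1 + 1 + 7 = 9 non-intercept terms (6.8 deaths each); one score makes 10 (6.1 each). The long list in SAP 5.9.5 could not all be fitted.

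**5. The primary test.** Protocol 8.5.1.2 has the same covariate wording, and SAP 6.2.3.2 stratifies by severity and country only. A van Elteren test with the score as an extra median-split stratum changes power by −3.3, −1.6, −0.1 and +3.5 points at AUC 0.50, 0.64, 0.70 and 0.78.

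**The case against.** The best defence is that the SAP hides nothing. It states its model in full, says where other variables go, and is to be finalised before the Day 90 lock (Section 9). The protocol never named its covariates, so its model could not be run as written and the SAP had to settle the matter. Protocol 8 leaves detailed methods to the SAP and sends deviations to the study report. Adjusting for the randomisation factors alone is defensible with about 61 deaths. The power gain rests on AUCs that the documents do not give. APACHE II is one of many candidates, beside age and SOFA, and because it covers the first 24 hours in the ICU it may predate ARDS onset and predict less well.

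Most of this stands, and it limits the point. A reader might infer from SAP 6.2.4.1 alone that all further adjustment has become optional. That is not so: SAP 5.9.5 says identified variables *will* be modelled, and only 6.2.4.1 says *may*. It is also true that the SAP's precision argument does not carry over to the log odds ratio, whose interval widens.

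Two things are left. Nothing in the SAP says that the narrower main model is a deliberate change, and a study report written after the results is a late place to say it. Nor can the planned sensitivity models add power to the hierarchical test.

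**Conclusion.** The point holds as an undeclared mismatch with a modest, avoidable loss of power on the first secondary test. At the design mortality rates and 272 patients, the loss is about 1-2 points if a baseline score has an AUC of about 0.64, 3 at 0.70 and 6 at 0.78, from a base of about 85-86%. It is about zero if the score predicts nothing. These sizes depend wholly on the assumed AUC; the direction and the near-zero cost of a useless score do not.

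A reader might go further and infer that the mortality test is invalid, that the sample size is wrong, or that the primary test has lost power in the same way. The documents support none of these. Type I error is similar with and without the score. The 272 comes from the Mann-Whitney calculation on VFDsurv. Extra stratification of the van Elteren test would cost power unless the score were strong. For the primary test only a note of the change is missing. Whether to use IWRS or Day 1 severity (SAP 5.2.2 against Protocol 4.6.2) is a separate, minor question.

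**What to change.** Before unblinding:

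1. In SAP 6.2.4.1, make the main logistic model treatment, severity, country and one pre-specified continuous pre-dose prognostic score that is already collected. APACHE II is one example; the choice among the collected scores is the sponsor's. State that this implements Protocol 8.5.2.1.
2. Give a treatment-blind rule for a missing score, such as the median over both arms, as a stated exception to the no-imputation rule in SAP 5.9.6.
3. Keep the present model as a sensitivity analysis, and reconcile *may* in 6.2.4.1 with *will* in 5.9.5.
4. In SAP 6.2.3.2, leave the van Elteren stratification as it is and note the departure from Protocol 8.5.1.2.

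If the sponsor prefers the present main model, the SAP should say so, give the reason, and name the covariates of one adjusted sensitivity model. That closes the documentation gap but not the loss of power.

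The cost is SAP wording only, with no new data. The odds ratio becomes conditional on the score (about 0.35 instead of 0.39 at AUC 0.70) and its log-odds interval does not narrow. The unadjusted rates and their difference are still reported under SAP 6.2.4.1. A useless score costs about 0.2 point or less in these simulations.

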#### ***6.2.4.2 Days Free Of Mechanical Ventilation Analysis***

The actual Total number of days free of mechanical ventilation (not the derived VFD scores which require additional conditions of UAB to be met) will be numerically summarised (excluding means and standard deviations) according to Treatment group (FP-1201-lyo/Placebo), Severity of ARDS (Moderate/Severe) and Overall. Separate supporting summaries by Country will be included.

These endpoints will be analysed using the same methods as for the primary efficacy variable, VFDsurv, using the Van Elteren hypothesis test as the distribution is likely to be non-normal and negatively skewed by patients who are assigned scores of zero (0) in the event of death.

#### ***6.2.4.3 Days Free Of Organ Failure, Renal Support And Vasoactive Support Analysis***

Totals derived will be numerically summarised and analysed as described in Section 6.2.4.2 above.

#### ***6.2.4.4 Length Of ICU 'Care Free' Stay/Hospital Stay Analysis***

Totals derived will be numerically summarised and analysed as described in Section 6.2.4.2 above.

#### ***6.2.4.5 Sequential Organ Failure Assessment (SOFA) Analysis***

Total scores and Change from baseline scores (Day 1 Pre-dose) assessed daily up to Day 14 and then at Day 21 and Day 28 (In or Out of the ICU) or Early Termination, together with the derived Last observation performed will be numerically summarised according to Treatment group (FP-1201-lyo/Placebo), Severity of ARDS (Moderate/Severe) and Overall using the FAS population. Separate supporting summaries by Country will be included.

The contributing Cardiovascular, Respiratory, Coagulation, Hepatic, Renal and CNS organ sub scores will be similarly presented.

The Total SOFA score at the Last observation performed will be analysed using an Analysis Of Covariance (ANCOVA) model (Ref 8) this will use change from baseline as the response variable and will include Treatment group (FP-1201-lyo/Placebo), Severity of ARDS (Moderate/Severe) and Country (1-8) as fixed effect factors. The Baseline value will also be used as a covariate term in the model.

Model assumptions of normality and constant variance will be investigated and if necessary an alternative model or data transformation will be substituted.

Model estimates (LS means and a 95% confidence interval for the treatment difference) will be presented. Homogeneity of treatment effect will be assessed by obtaining the difference in LS means together with 95% confidence intervals for the categories of ARDS severity using the ANCOVA model with the addition of a treatment by ARDS severity interaction term and displaying these in a Forest Plot.

Sub scores will not be analysed.

#### **6.2.4.6 Individual Organ Assessments Analysis**

##### **6.2.4.6.1 Cardiovascular Function**

Vasoactive support assessments recorded daily (Days 1 (Pre-dose) then daily on Days 2 - 28 (Day 28 In or Out of ICU) will be categorically summarised (Yes/No) with the derived Last observation performed, by Treatment group (FP-1201-lyo/Placebo), Severity of ARDS (Moderate/Severe) and Overall for each assessment time using the FAS population.

##### **6.2.4.6.2 Pulmonary Function**

Ventilation assessments recorded daily (Day 1 (Pre-dose/Day 1 dosing) then daily on Days 2 - 28 (Day 28 In or Out of ICU) will be numerically summarised (with the derived Last observation performed) using the actual values and change from baseline values by Treatment group (FP-1201-lyo/Placebo), Severity of ARDS (Moderate/Severe) and Overall for each assessment time using the FAS population. Separate supporting summaries by Country will be included.

Each of the gas exchange variables measured will be reported but the PaO2/FiO2 ratio change from baseline will be used to assess pulmonary function.

In addition, an Analysis of Covariance (ANCOVA) model, similar to the Total SOFA scores in Section 6.2.4.5 will include the PaO2/FiO2 ratio change from baseline value as the response variable at the Last observation performed assessment time.

Homogeneity of treatment effect will be assessed as for the SOFA score.

The Severity status and Change score classifications derived over the period of confinement within the ICU will be categorically summarised according Treatment group (FP-1201-lyo/Placebo), Severity of ARDS (Moderate/Severe) and overall using the FAS population.

The derived overall Change score classification (Improved, No Change, Worsened) will be analysed using the Cochran-Mantel-Haenszel hypothesis test including Severity of ARDS and Country as stratification variables. Statistical significance (p-value) overall will be displayed with the categorical summaries. Summary counts will be presented by severity of ARDS (Moderate/Severe).

